Context: Friedreich's ataxia (FRDA) is a rare autosomal recessive degenerative disorder characterized by ataxia, dysarthria, sensory loss, diabetes and cardiomyopathy. The discovery of the abnormal gene in FRDA and its product (frataxin) has provided insight into possible pathophysiological mechanisms and novel approaches to treatments in this disease. New therapies based on prevention of oxidant damage from abnormal mitochondrial function improve surrogate markers of disease such as muscle spectroscopy and echocardiography. While such methods for assessing disease progression may be useful, evaluation in clinical trials will require specific clinical outcome measures. Until recently, quantitative tools for clinical assessment of FRDA have been unavailable. For the past 10 years this group of investigators has collaborated on development of clinical measures that can quantitatively assess FRDA, particularly in children (1). While a large amount of measure refinement remains to be performed, the data from their collaboration provide a framework for further investigation and for creating a network for performing further clinical and translational research including clinical trials.

Objectives: To advance clinical care, research and therapeutic approaches in FRDA through the development and validation of clinical outcome measures in FRDA, collection of quantitative serial clinical data on patients and expansion of our established research network. A secondary aim is to investigate frataxin dipsticks (buccal cells swabs and blood samples) designed to measure frataxin protein. A third objective is to define the progression of physiological dysfunction in affected tissues in FRDA. The study aims to quantify impaired skeletal muscle oxidative phosphorylation (OXPHOS) using a magnetic resonance imaging (MRI) protocol to assess post-exercise creatine chemical exchange saturation transfer (CrCEST) and to understand changes in motor evoked potentials (MEP) in subjects with FRDA.

Study Design/Setting/Participants: This study will primarily take place at the Children's Hospital of Philadelphia (CHOP), with a select number of subjects only participating in the clinical testing at the University of Florida and University of California Los Angeles (UCLA). We expect to recruit approximately 110 children across all three sites and study each of them over a 3 year period. Children with a genetically or clinically confirmed diagnosis of FRDA will be offered participation.

Study Measures: For all 110 participants there will be biyearly assessments of a core set of clinical measures and quality of life assessment measures. These include: Friedreich's Ataxia Rating Scale (FARS), timed 9-Hole Peg Test (9HPT), Timed 25 Foot Walk (T25FW), Pediatric Quality of Life questionnaire (PedsQL), Activities of Daily Living (ADL) scales, Ataxia disability score, and two extended walking tests for 1 minute and 6 minutes. Also included are the Timed up and go (TUG), Berg Balance scale (BBS), 2 tests of the Composite Functional Cerebellar (CCFS), electronic pegboard, and the click test. At each visit, whole blood and buccal swab samples will be obtained to monitor frataxin levels.

12 of the study participants at CHOP will undergo annual MRI scan testing for the CrCEST protocol in addition to the core set of tests listed above.

30 of the study participants at CHOP will have annual MEP measurements using transcranial magnetic stimulation (TMS) in addition to the core set of tests listed above.

1 BACKGROUND INFORMATION AND RATIONALE

1.1 Introduction

Friedreich's ataxia (FRDA) is a rare autosomal recessive degenerative disorder characterized by ataxia, dysarthria, sensory loss, diabetes and cardiomyopathy. FRDA is a progressive neurodegenerative disorder with a prevalence of about 1 in 50,000 persons in the United States. The discovery of the abnormal gene in FRDA and its product (frataxin) has provided insight into possible pathophysiological mechanisms in this disease (1-3). An expanded GAA triplet repeat is found in both alleles of the FRDA gene in 97% of people with FRDA. This triplet repeat is located within an intron, leading to decreased RNA transcription and decreased levels of frataxin. While the basic-science-related understanding of FRDA has advanced rapidly, translational and clinical research has moved much more slowly. This reflects two aspects of FRDA. First it is uncommon-even large academic medical centers may only follow 10- 20 patients with this disorder. This requires that, in any clinical or translational study, multiple centers collaborate and assess patients in a coordinated manner. Secondly, until recently, quantitative tools for clinical assessment of FRDA have been unavailable. This has limited the ability of translational approaches to move forward and the initiation of therapeutic trials. Using recent support from the MDA and FARA, a group of investigators collaborated on development of clinical measures that can quantitatively assess FRDA (4). While a large amount of measure refinement remains to be performed, the data from their collaboration provides a framework for further investigation and for creating a network for performing further clinical and translational research including clinical trials. Still a major deficiency is the relative lack of sensitivity of measures in children, and their correlation with potential biomarkers.

Therapeutic interventions are aimed primarily at either 1) up-regulating expression of the frataxin protein (patients all have residual levels of normal protein and experimental approaches have demonstrated proof of principle of this approach with various small drugable molecules), or 2) ameliorating the pathogenic effects of low frataxin levels, namely a) reduced activities of key mitochondrial enzymes involved in energy metabolism that are dependent on Frataxin-dependent mitochondrial iron metabolism (FeS cluster-containing enzymes such as aconitase and OXPHOS enzyme complexes I, II and III, and possibly heme-dependent enzymes such as OXPHOS enzyme complex IV), and b) generalized oxidative stress in mitochondria and its negative consequences on mtDNA, proteins and membrane lipids.

Efficacy of these therapies can be monitored both by scoring clinically-defined neurologic parameters, and also by biochemical measurement of key mitochondrial enzymes, functions or metabolites or by genetic modifiers. Currently, genetic modifier studies have been limited to the lack of DNA samples linked to detailed clinical information that allows for stratification of the disease group based on disease severity and phenotypic variability. Frataxin levels will be a primary biochemical endpoint in therapeutic interventions designed to up regulate the steady-state levels of this protein. Moreover, upregulated frataxin levels will of necessity precede any other markers of clinical efficacy, including neurological scores. Therefore, tests to monitor these levels should be able to use tissue samples that can be obtained repetitively and non-invasively. Examples of such samples are oral epithelial cells obtained by non-invasive gentle cheek swabs and whole blood obtained by standard blood draws or finger prick sampling. Additionally, physiological abnormalities from frataxin deficiency in affected tissues can be monitored using imaging techniques, including ³¹P magnetic resonance spectroscopy (MRS) and MEP.

1.2 Compliance Statement

This study will be conducted in full accordance with all applicable Children's Hospital of Philadelphia, and participating sites (University of Florida and University of California Los Angeles) Research Policies and Procedures and all applicable Federal and state laws and regulations including 45 CFR 46, and the HIPAA Privacy Rule. Any episode of noncompliance will be documented.

The investigators will perform the study in accordance with this protocol, will obtain consent and assent (unless a waiver is granted), and will report unexpected problems in accordance with all participating sites' IRB Policies and Procedures and all federal requirements. Collection, recording, and reporting of data will be accurate and will ensure the privacy, health, and welfare of research subjects during and after the study.

1.3 Relevant Literature and Data

See references/ Appendix 1 of the attached grant.

2 STUDY OBJECTIVES

Overall Aim: To advance clinical care, research and therapeutic approaches in FRDA through the development of valid yet sensitive clinical and biochemical measures crucial to outcome assessment of children with Friedreich's Ataxia

2.1 Primary Objective (or Aim)

Aim 1: Identify markers of disease progression in children with FRDA and assess potential clinical measures of disease progression in the youngest subjects (n=110).

2.2 Secondary Objectives (or Aim)

Aim 2: Assess the biochemistry of frataxin deficiency in children with FRDA. Measure frataxin deficiency and downstream metabolic function. Understand how these biochemical markers change over time. Support genetic modifier studies and biomarker studies. Evaluate the clinical utility of measuring frataxin levels in easily-accessible tissue samples, cheek swabs, suitable for the repetitive testing needed to monitor efficacy of therapies designed to up-regulate levels of frataxin protein.

Aim 3: Define the progression of physiological dysfunction in affected tissues in children with FRDA. Use noninvasive testing to assess the physiological correlates of progression of FRDA.

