4.3 Buccal Swab Collection

Sterile, disposable Epicentre MasterAmp Buccal Swab Brushes will be used to isolate buccal cells (cells lining the mouth) from the inner cheek as suggested by the manufacturer. The procedure is very gentle and causes no discomfort. The inner cheeks are first gently cleansed by light brushing with a new moist, soft toothbrush and then rinsed with a sip of water. An Epicentre MasterAmp Buccal Swab Brush is then gently but firmly used to brush both cheeks, collecting a light layer of easily sloughed-off epithelial cells on the surface of the brush. Exfoliated cells are then transferred to ice-cold extraction buffer preloaded in a small sample collection tube. The sample is then immediately coded and processed for frozen storage in [name] laboratory. The specimen is analyzed by lateral flow assay and performed by a trained laboratory technician.

As with the frataxin blood sample, the cheek swab will be processed in [name] lab. Samples from other sites will again be shipped on dry ice according to proper guidelines. Samples will not be sent with any PHI. Again, the purpose of sending the samples to [name] lab at CHOP is to ensure that similar results are obtained on this assay across multiple locations. This is required to validate the assay.

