4.7 Primary and Secondary Endpoints

The primary goal of this study is to gather long-term serial quantitative clinical data using the measures validated during the three years of the study.

Aims 1: The primary endpoint (s) are the change in each of the clinical measures over time. The rate of change of each of these will be compared for responsiveness to change (SD of change/mean change).

Aim 2: Biochemical measures: The rate of change of frataxin and each platelet biomarker will be determined as primary endpoints. The rate of change over time will be determined to define which measures are most sensitive to disease progression.

Aim 3: Anatomical measures: The primary endpoints are the post exercise recovery time, Tau, for CrCest and the MEP size for MEP testing. The rate of change over time will be determined to define which measures are most sensitive to disease progression.

The secondary analyses are:

The rate of change of each measure the (neurological measures, biochemical measures and anatomic measures) as a function of age, GAA repeat length and sex, as determined by linear regression models

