5.2.2 Potential Benefits of Study Participation

This study will provide long-term data on quantitative measurements of disease progression in children that will provide natural history data for FRDA. This study will also test and validate a non-invasive approach to measuring frataxin protein which will be necessary for future clinical trials. It will also seek to identify metabolic and anatomical biomarkers required for clinical trials. Lastly, this proposal will further develop the infrastructure and support for evaluating new clinical outcome measures and biomarkers. Subjects will not benefit directly but their participation will contribute to the necessary clinical research required to support the advancement of therapeutics in FRDA.

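### Aim 2 sets out to evaluate cheek-swab frataxin for repeated monitoring, but no pre-specified analysis estimates the swab's within-child variability or separates swab from blood

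*Combined protocol and SAP*

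**What the plan says.** The objective is stated in several places. Section 2.2 places in Aim 2 the task to "Evaluate the clinical utility of measuring frataxin levels in easily-accessible tissue samples, cheek swabs, suitable for the repetitive testing needed" for following frataxin-raising treatments. The synopsis objectives state: "A secondary aim is to investigate frataxin dipsticks (buccal cells swabs and blood samples) designed to measure frataxin protein". Section 5.2.2 lists as a benefit: "This study will also test and validate a non-invasive approach to measuring frataxin protein which will be necessary for future clinical trials". Section 4.3 explains that swabs go to one laboratory "to ensure that similar results are obtained on this assay across multiple locations. This is required to validate the assay".

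On data, the synopsis says: "At each visit, whole blood and buccal swab samples will be obtained to monitor frataxin levels".

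On analysis, section 4.7 says for Aim 2: "The rate of change of frataxin and each platelet biomarker will be determined as primary endpoints". It gives the purpose as finding the measures most sensitive to progression. Section 4.8, Aim 2, then lists:
- descriptive summaries;
- models of marker values on age, GAA repeat length and sex;
- absolute and percent change over time, and its predictors;
- baseline marker level against clinical change;
- marker change as a predictor of clinical change.

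The only test-retest work in 4.8 is under Aim 1: a coefficient of variation in the first 5 subjects at the primary site, and comparisons between repeated trials of the timed walks, TUG and CCFS tests.

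**The concern.** A marker used to monitor a frataxin-raising therapy must show a treatment-induced rise above the ordinary visit-to-visit variation in an untreated child. The quantity needed is the within-child variability of the swab value and the change that can be told apart from it. A natural-history slope measures something else: a swab assay could be stable and precise, hence well suited to monitoring, and show little or no progression.

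If the plan is followed as written, swabs are collected at each in-person visit and the study can end without a swab-specific noise estimate. The analyst also has no rule on whether the frataxin endpoint means swab, blood or both. A future trial that wants to use the swab would lack the figure it needs for design.

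**Working it through.** The documents give no SD, power, effect size or repeatability margin for Aim 2, so there is no plan figure to reproduce. The check has two parts.

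**1. Objective against analysis**

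| Needed to judge the swab for repeated monitoring | Where the plan provides it |
|---|---|
| Swab identified as its own endpoint | Not in 4.7 or 4.8; tissue unnamed |
| Within-child variability of swab frataxin | Not planned; test-retest is in Aim 1 only |
| Smallest detectable change | Not planned |
| Consistency across sites | Stated as a purpose in 4.3; no statistic attached |
| Relation to genetic severity and clinical course | Planned in 4.8, tissue unnamed |

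Only the last row is covered, and it is indirect evidence.

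**2. What the planned samples could deliver**

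Inputs: 110 children (3.3.2); six dated visits at 0, 6, 12, 18, 24 and 36 months (3.1.2). The seventh, subject-dependent visit is not counted. Sections 3.1 and 4.9 describe six-monthly visits, but 3.1.2 lists none at 30 months; the count here follows 3.1.2.

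- Maximum number of visits with both samples: 110 × 6 = 660.
- Within-child degrees of freedom: 110 × (6 − 1) = 550, ignoring the one or two used by a common time trend.
- 95% limits for the SD, as multiples of its estimate: √(df/χ²₀.₉₇₅) and √(df/χ²₀.₀₂₅). For 550 df: √(550/616.9) = 0.944 and √(550/486.9) = 1.063.
- Smallest detectable between-visit change: 1.96 × √2 × SD = 2.77 × SD.

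The 550 df figure is a ceiling. Remote visits collect no samples (4.1), blood volume is capped by weight (4.2), and no dropout rate is given. The loss scenarios below are assumptions.

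| Scenario | df | 95% limits × SD |
|---|---|---|
| Complete data, common time trend | 550 | 0.94 to 1.06 |
| Complete data, child-specific slopes (110 × 4) | 440 | 0.94 to 1.07 |
| Assumed average of four samples per child (110 × 3) | 330 | 0.93 to 1.08 |
| Assumed average of three samples per child (110 × 2) | 220 | 0.92 to 1.10 |

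By site the position is weaker. UCLA and Florida together have at most 20 children (3.3.2). Assuming 10 at each with complete data, each site has 10 × 5 = 50 df and limits of 0.84 to 1.24. That supports description, not a formal comparison.

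**The case against.** **Aim 2 does produce evidence on utility.** The relations of frataxin to GAA repeat length and clinical course bear on clinical utility, the term section 2.2 uses, and a longitudinal mixed model has a within-child residual variance. This stands in part: a reader might infer that the objective gets no answer at all, and 4.8 does not support that. But nothing commits the study to reporting that variance, or says for which tissue.

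**Agreement with blood is not required.** A reader might infer that validation means swab-blood agreement. Section 2.2 does not ask for it, the two are different tissues, and the validation remark in 4.3 concerns similar results across locations. This objection stands; the association is supportive only.

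**The visits cannot give assay repeatability.** Visits are 6 to 12 months apart, so the SD combines assay noise, sampling noise and real biological change. No duplicate or short-interval swabs are scheduled. This stands and limits interpretation, but the between-visit SD is still relevant to a trial sampling at similar intervals.

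**A flat slope would be correctly labelled.** Section 4.7 calls its criterion sensitivity to progression, so the text does not imply that a flat slope will be reported as lack of utility. This stands. The gap is the missing estimate, not a misreading already in the plan.

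**The measures are exploratory.** Section 4.2 describes specimen collections this way, in its account of the blood dipstick. That does not withdraw the objective in 2.2 or the promise in 5.2.2, and 4.7 makes frataxin change a primary endpoint of Aim 2.

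**Conclusion.** The point holds in this form: evaluating the swab for repeated monitoring is a stated part of Aim 2, the planned analyses address it only indirectly, and no pre-specified analysis gives the swab's within-child variability or separates swab from blood. The change should be made, although this is a secondary aim and Aim 1 is unaffected.

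The planned samples could give the between-visit SD to within about 6% at best, and to within about 8 to 10% under the assumed losses. These figures assume roughly normal within-child errors on the analysis scale, a common within-child SD, and a time trend that the model captures. They describe between-visit variation only. The best-case interval should not be read as the expected precision.

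**What to change.** - **Section 4.7, Aim 2:** name swab frataxin and blood frataxin as separate endpoints. Section 4.2 mentions both a blood frataxin assay and a blood dipstick, so state which blood value is meant.
- **Section 4.8, Aim 2:** from a longitudinal mixed model with time, report the within-child between-visit SD or CV for swab, and for blood as comparator, each with a 95% interval. Give the smallest detectable between-visit change as 2.77 × SD. State that it mixes assay, sampling and biological variation and is not pure assay repeatability.
- **Supportive:** report the same-visit swab-blood correlation, allowing for repeated pairs within child, without making agreement a requirement.
- **By site:** compare CHOP with the other two sites descriptively only.
- **Denominators:** report how many children and visits contribute a swab, a blood sample and both, since remote visits yield none.

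The cost is a little more analysis work and a limited interpretation of the SD. No extra samples or visits are needed. Separating out pure assay repeatability would need duplicate or short-interval swabs, which are not scheduled and are not part of this request.

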3 INVESTIGATIONAL PLAN

3.1 General Schema of Study Design

Pediatric Subjects will be recruited from each site's ongoing practice and the Friedriech Ataxia natural history study and invited to participate in this study. [name] will recruit up to 90 children from his practice to participate at CHOP, and the remaining two sites, UCLA and University of Florida, will recruit up to 20 children in a similar manner to participate. Such subjects will return every 6 months for neurological measures, and biochemical measures (frataxin levels, platelet metabolic biomarkers). At each annual visit a select number of participants at CHOP will also complete tests assessing anatomical biomarkers. Data will be analyzed based on the change in measures over time to identify those that change serially in FA and the ability of disease features to predict such change.

3.1.1 Screening Phase

Subjects will be identified from natural history studies and clinical practices. Informed consent will be obtained by trained personnel at each site.

3.1.2 Assessment Phase

Visit 1 (0 months) Subjects will be assessed by medical history, neurological tests (FARS, Timed 25 foot walk (T25W), Timed 1 and 6 minute walks, Timed up and go (TUG), Berg Balance scale (BBS), 9 hole peg test (9HPT), PedsQL, ADL score and ataxia disability scale), biochemical tests (frataxin level, platelet metabolic biomarkers), and physiological testing (CrCEST, MEP). Data will be collected over a one day visit.

Visit 2. (6 months) Subjects will be assessed by medical history, neurological tests (FARS, Timed 25 foot walk (T25W), Timed 1 and 6 minute walks, TUG, BBS, 9HPT, PedsQL, ADL score, ataxia disability scale), and biochemical tests (frataxin level, platelet metabolic biomarkers). Data will be collected over a one day visit.

Visit 3 (12 months) Subjects will be assessed by medical history, neurological tests (FARS, Timed 25 foot walk (T25W), Timed 1 and 6 minute walks, Timed up and go (TUG), Berg Balance scale (BBS), 9 hole peg test (9HPT), PedsQL, ADL score and ataxia disability scale), biochemical tests (frataxin level, platelet metabolic biomarkers), and physiological testing (CrCEST, MEP). Data will be collected over a one day visit.

Visit 4. (18 months) Subjects will be assessed by medical history, neurological tests (FARS, Timed 25 foot walk (T25W), Timed 1 and 6 minute walks, TUG, BBS, 9HPT, PedsQL, ADL score, ataxia disability scale), and biochemical tests (frataxin level, platelet metabolic biomarkers). Data will be collected over a one day visit.

Visit 5 (24 months) Subjects will be assessed by medical history, neurological tests (FARS, Timed 25 foot walk (T25W), Timed 1 and 6 minute walks, Timed up and go (TUG), Berg Balance scale (BBS), 9 hole peg test (9HPT), PedsQL, ADL score and ataxia disability scale), biochemical tests (frataxin level, platelet metabolic biomarkers), and physiological testing (CrCEST, MEP). Data will be collected over a one day visit.

Visit 6 (36 months) Subjects will be assessed by medical history, neurological tests (FARS, Timed 25 foot walk (T25W), Timed 1 and 6 minute walks, Timed up and go (TUG), Berg Balance scale (BBS), 9 hole peg test (9HPT), PedsQL, ADL score and ataxia disability scale), biochemical tests (frataxin level, platelet metabolic biomarkers), and physiological testing (CrCEST, MEP). Data will be collected over a one day visit.

Visit 7 (subject dependent) Subjects will be assessed by medical history, neurological tests (FARS, Timed 25 foot walk (T25W), Timed 1 and 6 minute walks, Timed up and go (TUG), Berg Balance scale (BBS), 9 hole peg test (9HPT), PedsQL, ADL score and ataxia disability scale), biochemical tests (frataxin level, platelet metabolic biomarkers), and physiological testing (CrCEST, MEP). Data will be collected over a one day visit.

Data will be analyzed by [name] and collaborators. No subject visits occur during this time.

